IWQOL-Lite-CT	Impact of Weight on Quality of Life-Lite-Clinical Trials Version
Lilly	Eli Lilly and Company
LLT	Lowest-Level Term
MACE	major adverse cardiovascular event(s)
MedDRA	Medical Dictionary for Regulatory Activities
mITT	modified intent-to-treat
MMRM	mixed model for repeated measures
MRD	minimum required dilution
MTD	maximum tolerated dose
NAb(+/-)	neutralizing antibody (positive/negative)
PF	Physical Function(ing)
PG	plasma glucose
PGIS	Patient Global Impression of Status for Physical Activity
PHQ-9	Patient Health Questionnaire
PK	pharmacokinetic(s)
PT	Preferred Term
QTcF	Fridericia's corrected QT interval
QW	once weekly
REML	restricted maximum likelihood
SAE	serious adverse event
SBP	systolic blood pressure
SD	standard deviation

SF-36v2	Short Form-36 Version 2 Health Survey acute form
SI	Système International
SMQ	Standardized MedDRA Query
SOC	System Organ Class
SS	Safety Analysis Set
TBL	total bilirubin
TE ADA (+/-)	treatment-emergent anti-drug antibody (positive/negative)
TEAE	treatment-emergent adverse event
TIMP	Trial Issues Management Plan
T2DM	type 2 diabetes mellitus
UACR	urine albumin-to-creatinine ratio
ULN	upper limit of normal

Version History

This Statistical Analysis Plan (SAP) for Study I8F-MC-GPHM (GPHM) is based on the protocol dated 19 November 2020.

SAP Version History Summary

SAP Version	Approval Date	Change	Rationale
1	25 Mar 2021	Not applicable	Original version
2	07 Oct 2022	Details can be found in SAP Version History	Details can be found in SAP Version History
3	See date on Page 1	See below	See below

The key changes of the SAP Version 3 are summarized below:

1. In response to US Food and Drug Administration (FDA) feedback, clarified that the population-level summary for the “difference in response percentages between treatment conditions” is assessed by odds ratio (see Section [1.1.2.1](#)).
2. Clarified that placebo multiple imputation will be used for missing data imputation in Category 1 for treatment-regimen estimand if there are not enough retrieved dropouts to impute missing data in Category 2 (see Section [4.3.2.3](#)).
3. In response to US FDA feedback, added sensitivity analyses to evaluate the robustness of the primary efficacy results using different missing data imputation methods (see Section [4.3.2.4](#)).
4. Updated to add body weight at Visit 10 (Week 0) as an additional covariate to the mixed model for repeated measures (MMRM) models for the analyses of mean change in body weight, mean percent change in body weight, and mean change in body mass index (BMI) from Week -12 to Week 72. This covariate adjusts for body weight prior to randomization on the final outcome (see Section [4.4.2.1](#)).
5. Added exploratory endpoints to assess risk difference between tirzepatide maximum tolerated dose (MTD) and placebo arm for an unconditional effect in proportions of participants achieving body weight reduction targets (see Section [4.5](#)).

1. Introduction

Changes to protocol-planned analyses are described in Section [4.9](#).

1.1. Objectives, Endpoints, and Estimands

1.1.1. Objectives and Endpoints

Table GPHM.1.1. Objectives and Endpoints

Objectives	Endpoints
Primary	

To demonstrate that tirzepatide MTD is superior to placebo from randomization for the following (measured at 72 weeks):
 
 • Percent change in body weight AND • Proportion of participants with $\geq 5\%$ body weight reduction 	
 • Mean percent change in body weight • Percentage of study participants who achieve $\geq 5\%$ body weight reduction
Key Secondary (controlled for type I error)	

To demonstrate that tirzepatide MTD is superior to placebo from randomization for the following (measured at 72 weeks):
 
 • Maintaining body weight reduction achieved during the 12-week lead-in period • Body weight • Waist circumference 	
 • Percentage of study participants who maintain $\geq 80\%$ of the body weight lost during the 12-week lead-in period • Percentage of study participants who achieve: 
 ○ $\geq 10\%$ body weight reduction ○ $\geq 15\%$ body weight reduction ○ $\geq 20\%$ body weight reduction • Mean change in waist circumference (cm)
Additional Secondary	

Compare tirzepatide MTD QW with placebo from randomization for the following (measured at 72 weeks):
 
 • Body weight and BMI • Blood pressure 	
 • Mean change in body weight (kg) • Mean change in BMI (kg/m^2) • Mean change in 
 ○ systolic blood pressure (mmHg) ○ diastolic blood pressure (mmHg)

Objectives	Endpoints

 • Lipid parameters • Glycemic control • Insulin • Patient-reported outcomes 
Compare tirzepatide MTD QW with placebo from Visit 2 for the following (measured at 72 weeks):
 
 • Body weight and BMI • Waist circumference 	
 • Mean change in: 
 ○ Total cholesterol (mg/dL) ○ HDL-C (mg/dL) ○ Non-HDL-C (mg/dL) ○ LDL-C (mg/dL) ○ VLDL-C (mg/dL) ○ Triglycerides (mg/dL) ○ Free fatty acids (mg/dL) • Mean change in 
 ○ fasting glucose (mg/dL) ○ HbA1c (%) • Mean change in fasting insulin (pmol/L) • Mean change in 
 ○ SF-36v2 acute form Physical Functioning domain score ○ IWQOL-Lite-CT Physical Function composite score • Mean change in absolute body weight (kg) • Mean percent change in body weight • Mean change in BMI (kg/m²) • Mean change in waist circumference (cm)

Abbreviations: BMI = body mass index; HbA1c = hemoglobin A1c; HDL-C = high-density lipoprotein cholesterol; IWQOL-Lite-CT = Impact of Weight on Quality of Life-Lite-Clinical Trials Version; LDL-C = low-density lipoprotein cholesterol; MTD = maximum tolerated dose; QW = once weekly; SF-36v2 acute form = Short Form-36 Version 2 Health Survey acute form; VLDL-C = very low-density lipoprotein cholesterol.

1.1.2. Estimands

1.1.2.1. Estimands for Co-Primary Endpoints

The primary clinical question of interest is: What is the intervention difference between the once weekly (QW) tirzepatide MTD (10 mg or 15 mg) and placebo in mean percent change in body weight and proportion of participants who achieve $\geq 5\%$ body weight reduction from randomization to 72 weeks in participants without type 2 diabetes mellitus (T2DM), who have obesity ($\text{BMI} \geq 30 \text{ kg/m}^2$), or are overweight ($\text{BMI} \geq 27 \text{ kg/m}^2$) with at least 1 weight-related comorbid condition?

For Primary Disclosure of Study GPHM, Including Submission to the US FDA

The estimand is described by the following attributes:

- Population - Participants qualifying for study entry and randomization per protocol criteria.
- Co-primary endpoints - Percent change, from randomization to 72 weeks, in body weight AND participant status of achieving $\geq 5\%$ body weight reduction from randomization to 72 weeks.
- Treatment condition of interest - Tirzepatide MTD versus placebo, regardless of study drug adherence.
- Handling of intercurrent events (ICEs) - The ICEs leading to treatment discontinuation for any reason are addressed by the treatment condition of interest attribute and handled by treatment policy strategy as described in the International Council for Harmonisation (ICH) E9 (R1) Addendum. Further details can be found in Section 4.3.2.1.
- Population-level summary - Difference in mean changes between treatment conditions AND difference in response percentage between treatment conditions as assessed by odds ratio.

Rationale for Estimand

The estimand was requested by the FDA. It aims at reflecting how participants with obesity, or overweight with weight-related comorbidities, are treated in clinical practice, and it considers both safety and efficacy.

This *de facto estimand* is referred as the “treatment regimen” estimand in the latter sections of this document, which is equivalent to the “hybrid” estimand in the protocol.

For All Other Purposes

The estimand is described by the following attributes:

- Population - Participants qualifying for study entry and randomization per protocol criteria.
- Co-primary endpoints - Percent change from randomization to 72 weeks in body weight AND participant status of achieving $\geq 5\%$ body weight reduction from randomization to 72 weeks.

- Treatment condition of interest - Tirzepatide MTD versus placebo, excluding data after discontinuation of study drug.
- Handling of ICEs - The ICEs leading to treatment discontinuation for any reason are addressed by the treatment condition of interest attribute and handled by the hypothetical strategy as described in the ICH E9 (R1) Addendum.
- Population-level summary - Difference in mean changes between treatment conditions AND difference in response percentage between treatment conditions as assessed by odds ratio.

Rationale for Estimand

The estimand aims to reflect treatment efficacy in an envisaged scenario in which the ICEs leading to treatment discontinuation would not occur.

This estimand is referred to as the “efficacy” estimand in the latter sections.

1.1.2.2. Estimands for Secondary Endpoints

Table GPHM.1.2. Attribute Description of Estimands for Secondary Endpoints

Estimand for Secondary Endpoints	Population	Endpoint	Treatment Condition of Interest	Handling of Intercurrent Events	Population-Level Summary
Key secondary related to mean change	Same as estimands for co-primary endpoints	As described in Table GPHM.1.1	For submission to the US FDA, follow the same manner of the treatment regimen estimand in Section 1.1.2.1 ; for all other purposes, the same manner of the efficacy estimand in Section 1.1.2.1	For submission to the US FDA, follow the same manner of the treatment regimen estimand in Section 1.1.2.1 ; for all other purposes, follow the same manner of the efficacy estimand in Section 1.1.2.1	Difference in mean changes between treatment conditions
Key secondary related to percentage of participants meeting certain criteria					Difference in percentage of participants between treatment conditions
Other secondary related to mean change	Same as estimands for co-primary endpoints	As described in Table GPHM.1.1	Follow the same manner of the efficacy estimand in Section 1.1.2.1	Follow the same manner of the efficacy estimand in Section 1.1.2.1	Difference in mean changes between treatment conditions

Note: Unless otherwise specified, the attributes of estimands for supporting exploratory objectives will follow the same manner of the efficacy estimand in [Section 1.1.2.1](#).

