4.3.2. Main Analytical Approach

4.3.2.1. The Analysis Related to the Treatment Regimen Estimand

The analysis related to treatment regimen estimand will be conducted using data in the FAS.

The analysis for the mean percent change in body weight will be conducted utilizing ANCOVA. The response variable for the ANCOVA model will be percent change in body weight from randomization at 72 weeks. A logistic regression model will be used for the analysis of the percentage of participants achieving at least 5% body weight reduction obtained at the 72-week visit. Both models will include terms of treatment group, country/pooled country, and sex as fixed effects and baseline body weight as a covariate. The ANCOVA analysis will be conducted with hybrid imputation of missing body weight at 72 weeks (see Section 4.3.2.3 for details) and statistical inference over multiple imputation of missing data guided by Rubin (1987). For the

logistic regression, missing body weight data at 72 weeks will be imputed first, based on Section 4.3.2.3, then the continuous measurements will be categorized into status of achieving at least 5% body weight reduction (Yes or No).

With the aid of the ANCOVA model, the 2-sided 95% CI for mean change in percentage of body weight from baseline to the Week 72 visit between tirzepatide MTD and placebo will be derived.

With the aid of the logistic regression model, the 2-sided 95% CI and odds ratio for percentage of participants achieving at least 5% body weight reduction from baseline to the Week 72 visit between tirzepatide MTD and placebo will be derived.

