4.3.2.2. The Analysis Related to the Efficacy Estimand

The analysis related to the efficacy estimand will be conducted utilizing data in the EAS.

For the mean percentage of body weight change from randomization, an MMRM will be conducted. Restricted maximum likelihood (REML) will be used to obtain model parameter estimates, and the Kenward-Roger option will be used to estimate the denominator degrees of freedom. The response variable of MMRM will be the percent change in body weight from baseline values obtained at each scheduled postbaseline visit.

For the percentage of participants achieving at least 5% body weight reduction from randomization to the 72 weeks visit, a logistic regression model will be used with the response variable of the percentage of participants achieving at least 5% body weight reduction (Yes or No), with the missing value imputed using the predicted value from MMRM analysis followed by dichotomization. The terms for the logistic regression model will be the same as those for the treatment regimen estimand.

For the MMRM model, the independent variables of analysis model are treatment group, visit, and treatment-by-visit interaction; stratification factors (country and sex) as fixed effects; and baseline body weight as a covariate. An unstructured covariance structure will model the relationship of within-patient errors. If this model fails to converge, the following variance-covariance structures will be tested in order until convergence is achieved:

- heterogeneous Toeplitz
- heterogeneous first order autoregressive
- heterogeneous compound symmetry
- Toeplitz
- first order autoregressive, and
- compound symmetry.

The first covariance structure that converges will be used.

With the aid of the MMRM analysis, the 2-sided 95% CI for mean percent change in body weight from randomization to the 72 weeks visit for tirzepatide MTD compared to placebo will be derived and summarized. The resulting least-squares-mean estimates of mean percent change in body weight from baseline will be plotted by visit and by study treatment.

With the aid of the logistic regression model, the 2-sided 95% CI and odds ratio for percentage of participants achieving at least 5% body weight reduction from randomization to the 72-week visit for tirzepatide MTD compared to placebo will be summarized.

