4.4. Secondary Endpoint(s) Analysis

4.4.1. Key Secondary Analyses Subject to Type 1 Error Rate Control

Table GPHM.4.2. Secondary Measures Controlled for Type 1 Error

Objectives	Relative to the Efficacy Measure	Analysis Conducted in a Manner Similar to	Additional Information
Tirzepatide MTD QW is superior to placebo from randomization for maintaining body weight reduction achieved during the 12-week lead-in period (measured at 72 weeks)	Percentage of study participants who maintain $\geq 80\%$ of the body weight lost during the 12-week lead-in period	Logistic model in Section 4.3.2.1 for treatment regimen estimand and logistic model in Section 4.3.2.2 for efficacy estimand	
Tirzepatide MTD QW is superior to placebo from randomization for body weight reduction (measured at 72 weeks)	Percentage of participants achieving body weight reduction $\geq 10\%$, $\geq 15\%$, and $\geq 20\%$ from randomization at 72 weeks	Logistic model in Section 4.3.2.1 for treatment regimen estimand and logistic model in Section 4.3.2.2 for efficacy estimand	
Tirzepatide MTD QW is superior to placebo from randomization for waist circumference reduction (measured at 72 weeks)	Mean change in waist circumference (cm) from randomization at 72 weeks	ANCOVA model in Section 4.3.2.1 for treatment regimen estimand and MMRM model in Section 4.3.2.2 for efficacy estimand	LSM estimates will be plotted by treatment through 72-weeks.

Abbreviations: ANCOVA = analysis of covariance; LSM = least squares mean; MMRM = mixed model for repeated measures; MTD = maximum tolerated dose; QW = once weekly.

Decision will be guided by the 2-sided p-values in each objective, and details will be included in Section 2.1.

For submission of Study GPHM to the US FDA to support the registration of tirzepatide for chronic weight management, the key secondary efficacy assessment will be guided by the treatment regimen estimand, conducted using the same population as the primary analysis. Assessment of the key secondary objective will be conducted with hybrid imputation of missing data (see Section 4.3.2.3).

For other regulatory agencies, publications, and other purposes, the assessment of key secondary efficacy objectives may be guided by the efficacy estimand, using the same population as the primary analysis.

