Assess change for patient-reported outcome measurements change from Week -12 to Week 0	Mean change in patient-reported outcome measurements (Section 4.7.1)	Data from Week -12 to Week 0 will be included. Change from baseline to postbaseline values at each scheduled visit will be summarized. Within-treatment difference will be assessed by a Wilcoxon signed-rank test.
Compare tirzepatide MTD QW with placebo for patient-reported outcome measurements change from Week 0 to 72 weeks	Mean change in patient-reported outcome measurements (Section 4.7.1)	Data from Week 0 to 72 weeks will be included. An ANCOVA model with terms of treatment (tirzepatide MTD, placebo), country/pooled country, sex, and corresponding baseline score as a covariate will be used. Missing data will be imputed using LOCF.
Compare tirzepatide MTD QW with placebo for patient-reported outcome measurements change	Mean change in patient-reported outcome measurements (Section 4.7.1)	Data from Week -12 to 72 weeks will be included. An ANCOVA model with terms of treatment (tirzepatide MTD, placebo),

from Week -12 to 72 weeks		country/pooled country, sex, and corresponding baseline score as a covariate will be used. Missing data will be imputed using LOCF.
---------------------------	--	---

Abbreviations: ANCOVA = analysis of covariance; BMI = body mass index; EAS = Efficacy Analysis Set; HbA1c = hemoglobin A1c; HDL-C = high-density lipoprotein cholesterol; LDL-C = low-density lipoprotein cholesterol; LOCF = last observation carried forward; MMRM = mixed model for repeated measures; MTD = maximum tolerated dose; QW = once-weekly; VLDL = very low-density lipoprotein cholesterol.

In addition, the following endpoint analyses to assess the risk difference in proportions for an unconditional treatment effect (Ge et al. 2011) between tirzepatide MTD and placebo arm may be conducted:

- percentage of participants achieving at least 5% body weight reduction from randomization at 72 weeks
- percentage of participants achieving at least 10% body weight reduction from randomization at 72 weeks
- percentage of participants achieving at least 15% body weight reduction from randomization at 72 weeks
- percentage of participants achieving at least 20% body weight reduction from randomization at 72 weeks
- percentage of participants achieving at least 25% body weight reduction from randomization at 72 weeks

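### The key secondary responder estimands (SAP H2 to H5) are defined as a difference in percentages, but the planned between-arm estimate is an odds ratio, and the optional risk difference omits weight maintenance (H2)

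*SAP*

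**What the plan says.** **Estimand.** SAP Section 1.1.2.2, Table GPHM.1.2, gives the population-level summary for key secondary endpoints that count participants meeting a criterion as "Difference in percentage of participants between treatment conditions". In the SAP's numbering these are H2 (keeping at least 80% of the lead-in loss) and H3, H4 and H5 (at least 10%, 15% and 20% reduction from randomization). H6, waist circumference, is continuous and not at issue.

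**Analysis.** Section 4.4.1, Table GPHM.4.2, specifies for H2 and for H3 to H5: "Logistic model in Section 4.3.2.1 for treatment regimen estimand and logistic model in Section 4.3.2.2 for efficacy estimand". Its additional-information cell is empty for these rows. Section 4.3.2.1 states the model's output as "the 2-sided 95% CI and odds ratio for percentage of participants achieving at least 5% body weight reduction from baseline", and Section 4.3.2.2 as "the 2-sided 95% CI and odds ratio for percentage of participants achieving at least 5% body weight reduction from randomization". The models adjust for country or pooled country, sex and baseline body weight.

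**Risk difference.** Section 4.5 allows, without requiring, analyses to "assess the risk difference in proportions for an unconditional treatment effect". It lists reductions of at least 5%, 10%, 15%, 20% and 25%. The 80% maintenance endpoint is not listed.

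**Co-primary, for contrast.** Section 1.1.2.1 defines the summary for the 5% responder endpoint, under both estimands, as the "difference in response percentage between treatment conditions as assessed by odds ratio".

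**The concern.** A difference in percentages and a covariate-adjusted odds ratio are different quantities. The first is an absolute, marginal effect. The second is relative and conditional on the covariates, and it cannot be turned into the first without knowing the placebo rate. For H2 to H5 the plan names the first as its target and commits to estimating the second.

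The gap is widest for H2. Section 4.5 would at least permit a risk difference for H3 to H5, but it gives H2 none. Whether treatment helps people keep the weight they lost bears directly on the rationale for the lead-in design (Protocol Section 4.2). The trial could report that result without a between-arm estimate, with its uncertainty, on the scale that the SAP says it will use.

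What is at stake is the match between estimand and estimator, and the reported effect size. The success decision is not at stake.

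**Working it through.** **1. Passages side by side**

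| Endpoint | Stated summary | Committed between-arm estimate | Risk difference in 4.5 |
|---|---|---|---|
| At least 5% (co-primary) | Difference assessed by odds ratio | Odds ratio, 95% CI | Optional |
| H2, at least 80% maintained | Difference in percentages | Odds ratio, 95% CI | Not listed |
| H3 to H5, at least 10%, 15%, 20% | Difference in percentages | Odds ratio, 95% CI | Optional |

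The co-primary row is consistent. The other two are not. In Table GPHM.1.2 the cells for treatment condition and intercurrent events refer back to Section 1.1.2.1; the summary cell states its own measure and does not. The note under that table and Section 4.4.2 put exploratory analyses under the efficacy estimand by default, so no risk difference is clearly planned under the treatment regimen estimand.

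**2. The plan's own binary figure**

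SAP Section 5 claims more than 90% power for the 5% endpoint. Inputs: 20% versus 46%, 300 per arm, 25% dropout, two-sided 0.05, chi-square test.

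- Evaluable per arm: 300 × 0.75 = 225. Pooled rate: (0.20 + 0.46)/2 = 0.33.
- Null standard error: √(2 × 0.33 × 0.67/225) = 0.0443.
- Alternative standard error: √((0.20 × 0.80 + 0.46 × 0.54)/225) = 0.0426.
- z = (0.26 − 1.96 × 0.0443)/0.0426 = 4.06, so power is about 99.998%.

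The claim reproduces. It is the only binary power figure given; there is none for H2 to H5.

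**3. The two measures at those rates (illustration only)**

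- Risk difference: 0.46 − 0.20 = 26 points. At 225 per arm the Wald 95% interval is 26.0 ± 1.96 × 4.26, or about 17.6 to 34.4 points.
- Odds ratio: (0.46/0.54)/(0.20/0.80) = 3.41. At 225 per arm the 95% interval is about 2.24 to 5.18.

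**4. An odds ratio does not fix the difference**

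Hold the odds ratio at 3.41 and vary the placebo rate b. The treated rate is 3.41b/(1 − b + 3.41b). The placebo rates below are assumptions, except 20%, which is the planning rate for the 5% endpoint.

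| Placebo rate | Difference (points) |
|---|---|
| 2% | 4.5 |
| 5% | 10.2 |
| 10% | 17.5 |
| 20% | 26.0 |
| 40% | 29.4 |

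**5. Adjustment moves the two further apart**

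Under a logistic-normal model with an assumed prognostic standard deviation of 0.5, 1.0 or 1.5 on the logit scale, the same marginal 20% versus 46% corresponds to a conditional odds ratio of 3.63, 4.29 or 5.42. The documents give no value for that standard deviation.

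**The case against.** The strongest reply is that this is an unfinished edit. The SAP Version History says: "In response to US Food and Drug Administration (FDA) feedback, clarified that the population-level summary" for the response endpoints is assessed by odds ratio, and it ties that change to Section 1.1.2.1. H2 to H5 go to the same type of model, so the simplest explanation is that one table cell was missed. This stands as a reading of intent: nothing shows that the sponsor meant to make a risk difference primary, and adding the odds-ratio qualifier would remove the inconsistency. It does not change what the current text says. The same SAP version added the risk differences as a separate, unconditional effect, so the plan itself treats the two measures as distinct.

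A second reply is that Section 4.1 has percentages tabulated for categorical measures, so a reader can subtract. That stands in part: it would be wrong to infer that H2 will be seen only through an odds ratio. But a subtraction has no confidence interval, and the SAP does not say that the descriptive percentages use the imputed data. With 25% dropout assumed in planning, a crude difference need not estimate either estimand.

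A third reply is that decisions rest on two-sided p-values. This stands in full: an odds ratio of 1 and a risk difference of 0 are the same null hypothesis.

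**Conclusion.** The point holds as a mismatch between estimand and estimator for H2 to H5. No between-arm difference with a confidence interval is planned for H2. For H3 to H5 one is optional, exploratory and, by default, under the efficacy estimand only. P-values, sample size, power and type 1 error are untouched.

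Its size cannot be given for the endpoints concerned, because the documents state no planning rates for them. The 26 points against an odds ratio of 3.41 comes from the 5% co-primary and only illustrates how the measures differ. The conditional odds ratios also rest on an assumed covariate strength.

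Three stronger readings are tempting and not supported:

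- That the 5% co-primary is also mismatched. Its summary is explicitly defined through the odds ratio under both estimands.
- That the odds ratio overstates the effect by a known amount for H2. Neither document sets a risk ratio as a target or gives a rate for H2.
- That H2 carries extra weight as the first test after the co-primaries. It is first in the list of key secondary hypotheses, but the testing order is in Figure GPHM.2.1, which is not shown in the text reviewed.

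**What to change.** In Table GPHM.4.2, use the empty additional-information cells for H2 and for H3 to H5 to state that the covariate-adjusted risk difference with 95% confidence interval will be reported, by the method already cited in Section 4.5:

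- under the treatment regimen estimand, calculated in each imputed data set and pooled over the multiple imputations, with the pooling rule stated;
- under the efficacy estimand, on the same data as the logistic model of Section 4.3.2.2.

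Keep the logistic model for the test and the odds ratio as an accompanying estimate. Make Section 4.5 agree, so that the 10%, 15% and 20% items are no longer optional there and the 80% maintenance endpoint is covered. Editing Section 4.5 alone would leave Tables GPHM.1.2 and GPHM.4.2 in disagreement. A risk difference for the 5% co-primary is useful optional reporting, not a correction.

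The minimum alternative is to add the odds-ratio qualifier to the Table GPHM.1.2 row. That restores consistency but leaves H2 with no planned absolute between-arm effect, so it is the weaker choice.

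The cost is SAP wording plus programming and output for four endpoints under two estimands, with pooling under one of them. No new data or participants are needed. Protocol Section 9.4.3.2 already leaves the key secondary methods to the SAP.
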